#### 8.5 EEG and ECG

EEG and ECG may cause skin irritation. This risk will be minimized by following the standard procedures of the NIH EEG lab.

#### 8.6 Neuropsychological and mood testing

Neuropsychological and mood testing have minor risks, including boredom and frustration. Some patients may be disturbed by test results, or by questions about issues such as depression and suicide risk. Counseling will be provided under the supervision of the psychiatrist co-investigator should this occur.

#### 8.7 Genetic Testing:

Risks of genetic testing include emotional distress due to learning about increased risk of disease, and problems, such as with insurance or employment discrimination. All data from this protocol will be kept confidential. In addition, the polymorphisms to be tested for are still undergoing study and have not definitely been associated with any specific illnesses or shown to have any clear medical implications.

### 9. Subject Monitoring

#### 9.1 Parameters to be monitored

Patient reports of seizure frequency, adverse events and toxicity at regular phone/secure email/computer contact. Clinical exam, laboratory studies, seizure calendars, adverse events and toxicity reports and Hamilton Depression rating scale at clinic visits.

#### 9.2 Toxicity tables/ criteria to be used

Toxicity will be graded according to the NCI Common Terminology Criteria for Adverse Events (appendix). Dose limiting toxicities will be considered any NCI grade 3 toxicity felt to be probably or definitely related to study medication; grade 4 or 5 toxicity judged to be possibly, probably or definitely related to study medication by the safety monitor.

In the event of a Grade 3 toxicity felt to be probably or definitely related to study medication by the study investigator or safety monitor a one-step dose reduction will be initiated (i.e., from 240 to 160 milligrams per day) until the toxicity resolves to Grade 0 or decreases to Grade 1. If NCI Common Terminology Grade 4 toxicity is felt to be possibly, probably or definitely related to study medication by the study investigator, the patient will be withdrawn from treatment. All dose

changes and/or dose interruptions will be recorded on case report forms.

### 9.3 Criteria for Breaking the Blind and Premature Termination or withdrawal

Criteria to be used to decide whether a report or test result requires intervention include Grade 3 NCI CTC toxicity, a laboratory test twice the upper limit of normal, an abnormal finding on EEG or ECG not present at baseline, an increase of 7 on the Hamilton Depression Scale. Intervention will be determined by the safety monitor and may include consultation, additional studies, or withdrawing the patient from the protocol.

The blind for an individual may need to be broken even for non-serious, expected, or unrelated AEs or as requested by local regulatory authorities or where, in the view of the safety monitor, knowledge of the identity of the study drug is essential to appropriately manage an adverse event.

Patients will be removed from the study if they become pregnant, are unable to continue to cooperate, or have an alteration in clinical status, other than that related to their epilepsy, needing medical intervention. Patients may withdraw from the trial at any time at their own request. The Investigators may withdraw a subject for safety or behavioral reasons.

## 10. Outcome Measures

The primary outcome measures for drug efficacy will be:

Mean difference in seizure frequency comparing the active and placebo periods.

Secondary outcome measures for efficacy will be:

Proportion of patients with  $\geq 50\%$  lower seizure rate on PRX-00023 than placebo

Hamilton Depression and Anxiety Rating scales

Performance on neuropsychological testing scales

Outcome measures for safety will include:

Columbia Suicide Severity Rating Scale

Hamilton Depression Rating Scale

Clinical examination

CBC and clinical chemistry studies

ECG

Adverse event reports

Seizure Calendars

## 11. Statistical Analysis

### 11.1 Analysis of Primary Endpoint

Analysis of variance will be used to test for a treatment order effect. A carry-over effect is unlikely due to the long washout period. A paired samples Student's T-test will then be used to compare seizure frequencies during placebo and active treatment periods (see sample size calculation below). If the carry-over effect is significant, a two group T-test will be applied separately for each period.

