## 6. Subjects

### 6.1 Description of Study Population

The study will accrue up to thirty patients aged 18 to 65 inclusive with localization-related epilepsy with the goal of obtaining 20 completers, unless a carry-over effect is detected, in which case 24 completers would be required (see statistical analysis section 11. 4 and 11.41).

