### 11.4 Sample size and power calculation

We assume that the mean difference between drug and placebo will be a 15% lower seizure rate, (representing a 30% improvement on drug versus 15% improvement on placebo versus baseline), and that the standard deviation of difference is 22%.

Based on a paired t-test, the estimated sample size is 19 to obtain 80% power at a significance level of 0.05. In order to balance the two arms we will accrue patients until 20 completers have been obtained. We request a total of 30 subjects to take into account a possible 20% dropouts.

Paired t-test of mean difference equal to zero

	1	2	3	4
Test significance level, $\alpha$	0.050	0.050	0.050	0.050
1 or 2 sided test?	2	2	2	2
First condition mean, $\mu_1$	30.000	30.000	30.000	30.000

Second condition mean, $\mu_2$	15.000	15.000	15.000	15.000
Mean difference, $\mu_d = \mu_1 - \mu_2$	15.000	15.000	15.000	15.000
Standard deviation of differences, $\sigma_d$	22.000	23.000	20.000	25.000
Effect size, $\omega =  \mu_d  / \sigma_d$	0.682	0.652	0.750	0.600
Power ( % )	80	80	80	80
n	19	21	16	24

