#### 11.41 Independent period analysis

Based on calculations by the NINDS statistician, 24 completers would be needed in the event of detection of a carryover effect. If we detect a carryover effect, the additional sample size of 24 patients will have 80% power to detect a 45% decrease in seizure frequency in the PRX 00023 group, versus 15% in the placebo group, assuming the 25% common standard deviation.

Alpha = 0.050  
 Power = 0.800  
 Model = Two Sample t-test  
 Effect Size = 1.200  
 Pooled S.D. = 0.250  
 Mean(01) = 0.450  
 Mean(02) = 0.150

GROUP 1	GROUP 2	POWER
2	2	0.114
3	3	0.207
4	4	0.299
5	5	0.386
6	6	0.468
7	7	0.541
8	8	0.608
9	9	0.667
10	10	0.718
11	11	0.763
12	12	0.802

Total Sample Size = 24

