#### 11.5 Accrual number request

In order to accrue 24 subjects, we are requesting a total potential sample size of 30. This should account for patients who do not have enough seizures to qualify during baseline, as well as dropouts.

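### Section 11.1 can be read as letting a carry-over pre-test replace the primary paired t-test, with no rule for the fallback; on that reading type I error is about 7.6% to 9.2% at an assumed 0.05 pre-test

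*Combined protocol and SAP*

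**What the plan says.** Section 11.1 begins with an analysis of variance for an order effect and comments: "A carry-over effect is unlikely due to the long washout period". It continues: "A paired samples Student's T-test will then be used to compare seizure frequencies during placebo and active treatment periods". It ends: "If the carry-over effect is significant, a two group T-test will be applied separately for each period". It gives no significance level for the order test, does not name the period that decides, and does not say how two period results combine or share alpha.

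Section 11.41 sizes the two-group comparison as a single two-sample t-test at alpha 0.05 with 12 per group: "the additional sample size of 24 patients will have 80% power to detect a 45% decrease in seizure frequency", against 15% on placebo, SD 25%. Section 11.42 defines the analysis populations and adds no decision rule.

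The number of completers is tied to the same test. Section 6.1 sets recruitment "with the goal of obtaining 20 completers, unless a carry-over effect is detected, in which case 24 completers would be required", and 11.41 agrees: "24 completers would be needed in the event of detection of a carryover effect". Section 11.4 says: "In order to balance the two arms we will accrue patients until 20 completers have been obtained". Section 11.5 says: "In order to accrue 24 subjects, we are requesting a total potential sample size of 30". Section 16 describes blinded data review and no interim analysis.

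**The concern.** If a test on the trial data chooses the primary test, the error rate of the whole procedure is what counts, not that of each branch. A carry-over test on patient totals is correlated with each single-period comparison. With no true carry-over, it is significant only when one sequence group happens to have higher seizure rates than the other. That same imbalance then enters the between-group test in both periods. It favours the drug in one period and placebo in the other, so the fallback tends to give two results that point in opposite directions, often with one of them significant. Nothing in the plan says which is the trial's answer.

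The primary efficacy hypothesis in 5.1, sized in 11.4 at two-sided 0.05, is at stake. Two analysts could reach different conclusions from the same data.

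**Working it through.** **Inputs.** From 11.4: difference 15 points, SD of difference 22, two-sided alpha 0.05, 20 completers (10 per sequence). From 11.41: SD 25 per group, 30-point difference, 12 per group. Assumed because the plan is silent: pre-test level 0.05, with 0.10 as an alternative; order test as a two-sample t-test on patient totals; normal outcomes; no true treatment, carry-over or period effect when computing type I error.

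**The plan's own figures reproduce.** Exact noncentral-t calculations give n = 19 for the paired test (SD 22) and power 0.802 for the two-group test at 12 + 12.

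**Correlation.** If SD 22 and SD 25 are on one scale, correlation = 1 − 22²/(2 × 25²) = 0.613. The SD of a patient total is 25 × √(2 × 1.613) = 44.9.

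**Type I error if the fallback replaces the paired test.** With equal variances and normal data, a patient's total and difference are independent, so the paired test keeps its 5% when the pre-test does not trigger. Simulation (200,000 trials) shows how often the fallback rejects once the pre-test has triggered by chance. For pre-test 0.05 / 0.10:
- Period 1 significant: 57% / 39%
- at least one period significant: 90% / 66%
- both significant in the same direction: essentially 0%

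Overall error = (1 − a) × 0.05 + a × (fallback rejection rate), where a is the pre-test level:

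| Rule | a = 0.05 | a = 0.10 |
|---|---|---|
| Period 1 decides | 0.0475 + 0.05 × 0.57 = 0.076 | 0.045 + 0.10 × 0.39 = 0.084 |
| Either period at 0.05 | 0.0475 + 0.05 × 0.90 = 0.0925 | 0.045 + 0.10 × 0.66 = 0.111 |
| Both periods, same direction | about 0.048 | about 0.045 |
| Paired test only, no switch | 0.050 | 0.050 |

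Direct simulation of the whole procedure agrees: 7.6% / 8.4%, 9.2% / 11.1%, 4.8% / 4.5% and 5.0%. Testing each period at 0.025 and accepting either still gives 7.9% / 8.5%.

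**Sensitivity to the assumptions.**
- Zero correlation: 6.3–6.8% (Period 1) and 7.8–9.1% (either).
- Skewed counts, with assumed patient and period variation, over both pre-test levels: 5.3–7.7% (Period 1) and 6.3–10.3% (either), against 3.6–4.7% for the paired test alone.
- Order effect tested as a period effect: 5.0–5.5%.

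**What the pre-test and fallback can detect.** A 15-point carry-over shifts one sequence's totals by 15. The standard error is 44.9 × √(2/10) = 20.1, so the ratio is 0.75 and power is 11% (19% at a 0.10 pre-test). At 12 per group, the two-group test has 80% power for 30 points but 29% for the planned 15.

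**Washout.** Four weeks at a 13.5-hour half-life is 28 × 24/13.5 = 50 half-lives; six weeks at 9.8 hours is 42 × 24/9.8 = 103.

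**Completers.** Allowing 20% dropout, 20/0.8 = 25 and 24/0.8 = 30. The request for 30 therefore matches 24 completers, although 11.4 attaches it to 20. Paired power for 15 points is 82% (SD 22) or 72% (SD 25) at 20 completers, and 89% or 80% at 24.

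**The case against.** The strongest reply is textual. Section 11.1 says without condition that the paired test will be used, and never says the two-group tests come instead. If they are only added, the primary test holds its 5%. That stands as a possible reading, so replacement should not be treated as settled. The stand-alone sizing in 11.41 makes it the more natural reading, but a sizing calculation does not define the primary analysis.

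A reader might also infer that the error rate is 11%, about double the nominal level. That needs both a 0.10 pre-test and an either-period rule. The only level in the documents is 0.05, and 11.41 sizes a single two-group test, which fits one deciding period better.

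A reader might further infer that 11.5 fixes 24 completers outright, or that the plan hides an interim analysis. The request for 30 can equally be a ceiling covering the contingent 24. The statement that no interim analysis is planned sits in the safety-monitoring section, and a conflict arises only if carry-over is tested at 20 completers to decide whether to continue. What remains is that the four sections do not give one target and must be reconciled.

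Finally, this is a pilot, carry-over is called unlikely, and with a 0.05 pre-test the fallback would run by chance in about one trial in twenty. That limits the practical weight. It does not supply the missing rule, and it is also a reason not to keep the switch.

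**Conclusion.** The concern holds in a limited form. Section 11.1 can be read as a two-stage procedure, 11.41 supports that reading, and no section supplies a pre-test level, deciding period or division of alpha. On that reading, with a totals test at an assumed 0.05, type I error is about 7.6% if Period 1 decides and 9.2% if either period counts (8.4% and 11.1% at 0.10). Other readings keep it near 5%.

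The missing rule is certain; the size of the inflation is conditional. It rests on normal outcomes, an unstated pre-test and a correlation built from two SDs that come from separate calculations. The default paired test is sound, so this should be fixed but does not undermine the design.

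**What to change.** In 11.1, replace the last sentence with:

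> The primary analysis is the within-patient comparison of active and placebo periods, two-sided alpha 0.05. It will not be replaced on the result of any order or carry-over test. The Period 1 between-group difference with its 95% CI is a sensitivity analysis only.

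Name one method in advance. The paired t-test, as now planned, uses only patients with both periods. A model with treatment and period fixed and patient random can also keep the one-period patients whom 11.42 places in the ITT population. The two are therefore not interchangeable, and the choice should be reconciled with 11.42.

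In 6.1 and 11.41, delete the condition on detected carry-over. State one completer target in 6.1, 11.4, 11.41 and 11.5, with the matching power given above. Either 20 or 24 is defensible. The 12 + 12 scans in 11.22 should not be used to justify 24, because they include on-treatment scans while 7.582 describes one scan before study drug. Relabel the 11.41 table as power for the Period 1 sensitivity estimate: 80% for 30 points, 29% for 15.

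**Cost.** These are text edits, with no new visits and no accrual above 30. If 24 is chosen, reaching it is not assured: 30 × 0.8 = 24 leaves no room for the baseline failures that 11.5 also counts.

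**Downside.** If carry-over is real, the primary estimate is biased and only the sensitivity analysis would show it. A 15-point carry-over would halve a 15-point effect to 7.5. At 24 completers, power is then 32% for the paired test or 36% with period in the model, against 39–44% for the current rule on its permissive readings and 25–28% if both periods must agree. The plan calls carry-over unlikely, and a washout of at least about 50 half-lives argues against a pharmacokinetic one, though not against other kinds.

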### 7.51 Baseline:

Baseline phase may occur concurrent with screening procedures and may last up to 6 weeks. During baseline, patients will record seizures on a seizure calendar, while on their baseline treatment with one or two AEDs. They will be eligible for this study if they have at least four seizures during a 6-week baseline phase. If patients have 4 seizures in less than six weeks, they do not need to wait the entire 6-weeks to begin Period 1 of the treatment phase. No changes in

patients' baseline AEDs will be allowed during this period, or subsequent study phases. Patients who use sublingual lorazepam for seizure clusters may continue to do so.

During the Baseline phase the following tests (described in section 7.57 and 7.58) will be performed (unless previously completed, as noted):

Columbia Suicide Severity Rating Scale

Neuropsychological testing

Mood testing

Measurement of plasma AED levels, if assay available

Pregnancy test

EEG

18F-FCWAY PET to measure 5HT1A receptor binding (if not already performed)

Saliva samples to test for polymorphisms in SERT, TPNH, COMT, BDNF and GABA genes that have been associated with psychiatric disorders and epileptogenesis (if not previously performed)

Blood samples for cortisol and ACTH level will be obtained at the time of PET (if performed).

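### The carry-over fallback in 11.1 tests unadjusted seizure frequency while 11.41 sizes it on percent decrease; one baseline-adjusted outcome should be defined for both

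*Combined protocol and SAP*

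**What the plan says.** Section 10 defines the primary outcome as "Mean difference in seizure frequency comparing the active and placebo periods", with no reference to baseline. Section 11.1 compares seizure frequencies by a paired t-test and then gives the carry-over branch: "If the carry-over effect is significant, a two group T-test will be applied separately for each period". Neither section names a covariate or a change score for seizures. Section 11.21, by contrast, brings the baseline visit into the analysis of mood and neuropsychological scores.

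The baseline data exist. Section 7.51 states: "During baseline, patients will record seizures on a seizure calendar, while on their baseline treatment with one or two AEDs". The phase lasts up to six weeks but may end once four seizures have occurred (7.4 and 7.51). Entry sets a floor of four seizures in six weeks and no ceiling (6.2).

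Section 11.41 sizes the fallback at 24 completers "to detect a 45% decrease in seizure frequency in the PRX 00023 group, versus 15% in the placebo group", with a common SD of 25%. Section 11.4 describes the percentages in the main sizing as "representing a 30% improvement on drug versus 15% improvement on placebo versus baseline".

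**The concern.** In the carry-over branch the comparison is between different patients, about 12 against 12. With a floor but no ceiling on entry frequency, much of the spread in raw seizure frequency may be stable difference between low- and high-frequency patients, which a baseline rate can partly remove. The test named in 11.1 leaves it in the error term. The power claimed in 11.41 is for a different quantity, with a different SD.

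If the branch is reached, it supplies the primary result. The test could have much less than 80% power, and chance imbalance in seizure frequency between two small groups could obscure a real effect in that one trial. Whether a pre-test should select this branch at all is a separate question.

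**Working it through.** **1. The plan's own figure.** Inputs from 11.41: means 0.45 and 0.15, "Pooled S.D. = 0.250", alpha 0.05, 12 per group. Sidedness is not stated there; the table in 11.4 gives 2 in the row "1 or 2 sided test".

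- d = (0.45 − 0.15)/0.25 = 1.20
- Noncentrality = d√(n/2) = 1.20 × √6 = 2.94, with 2n − 2 = 22 df
- Two-sided power = 0.802

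All eleven rows of the 11.41 table match to three decimals, so 24 is correct on the percent-decrease scale.

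**2. The same effect on raw frequency.** Take the baseline mean as 1. Group means are 0.55 (active) and 0.85 (placebo), a difference of 0.30. With between-patient CV c in each group, the pooled SD is c × √((0.55² + 0.85²)/2) = c × √0.5125 = 0.716c. An SD of 0.25 needs c = 0.25/0.716 = 0.35. The documents give no CV, so a range is assumed:

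| CV | SD | d | Power, 12 v 12 |
|---|---|---|---|
| 0.5 | 0.358 | 0.838 | 50% |
| 0.75 | 0.537 | 0.559 | 26% |
| 1.0 | 0.716 | 0.419 | 17% |
| 1.5 | 1.074 | 0.279 | 10% |

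**3. What adjustment can recover.** Baseline adjustment multiplies the error variance by 1 − ρ², where ρ is the within-group correlation of baseline and on-treatment rate. The share removed is 9% at ρ = 0.3, 25% at 0.5, 49% at 0.7 and 64% at 0.8. Removing more than half needs ρ above √0.5 = 0.707. The documents give no ρ.

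**4. Simulation.** Assumed inputs: median 6–10 seizures per 28 days, between-patient log-SD 0.6–1.0, phase-to-phase CV within patient 0.2–0.3. Counts are gamma-Poisson over 90 days, entry needs at least four seizures in 42 days, and the true rate is multiplied by 0.55 on active and 0.85 on placebo, 12 v 12. With at least 1,500 trials per setting, the Monte Carlo standard error is at most √(0.25/1500) = 1.3 points. Power:

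| Test | Full 6-week baseline | Baseline stops at fourth seizure |
|---|---|---|
| t-test, raw frequency (baseline unused) | 12–33% over both rules | |
| t-test, log rate (baseline unused) | 17–37% over both rules | |
| t-test, percent change from baseline | 37–60% | 26–37% |
| Log rate adjusted for log baseline rate | 41–67% | 30–50% |

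The adjusted model gained 0–13 points over percent change. Its type I error was 4–6%. On the log scale, adjustment cut the variance of the treatment comparison by roughly 17–75%; in one set of 16 settings the cut was under half in 9.

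**5. A second set of assumptions.** Mean 3 seizures per week, CV 0.5–1.5, a 12-week period, and patient-to-patient variation in response (log-SD 0.3 or 0.6). Power was 9–37% for raw frequency, 18–56% for percent change, and for the adjusted log model 28–61% (full baseline) or 23–47% (stopped). The correlation on the raw scale was 0.48–0.88 with a full baseline and 0.33–0.73 with a stopped one. In one setting percent change and the adjusted model were level (52.8% v 52.5%). At CV 0.5 with a stopped baseline and response log-SD 0.3, percent change did no better than raw frequency (32.7% v 33.5%).

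**The case against.** The strongest defence is that 11.41 shows what the fallback was meant to test. If the t-test is run on percent decrease, each patient's baseline is already in the outcome, and the gain from the adjusted model is only 0–13 points. This stands as a limit on the size of the problem. It does not settle the text, because sections 10 and 11.1 say frequency and no section defines a percent-change outcome for analysis.

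Second, going from a raw t-test to an adjusted log model makes two changes. The log scale alone moves power from 12–33% to 17–37%, so not all of the gain comes from the baseline term. That is right, though most of the rise appears only when the baseline is used.

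Third, a baseline that may stop at four seizures is a noisy covariate. The stopped-baseline results above allow for this.

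Fourth, the branch may never be used. Section 11.1 calls carry-over unlikely, and the shortest washout is 4 × 7 × 24 = 672 hours, about 50 times the longest quoted half-life of 13.5 hours. That limits how often the point matters. Even so, 6.1 and 11.41 both plan for the branch with 24 completers.

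**Conclusion.** The point holds as a mismatch and a correctable loss of power. Sections 11.1 and 11.41 do not define the same outcome for the fallback, and the 80% in 11.41 describes a raw-frequency test only if the between-patient CV is about 0.35. Under the first set of assumed inputs, power is about 12–33% as 11.1 is worded and 30–67% with the adjusted log model. Every rate, CV and correlation here is assumed, because the documents give none.

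A reader might infer three stronger things that the documents do not support:

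- That the plan ignores baseline altogether. The sizing in 11.41 is on percent decrease, and 11.4 ties its matching percentages to baseline.
- That most of the available precision is thrown away. That needs ρ above 0.707, and the variance reduction of roughly 17–75% lies on both sides of one half.
- That the unadjusted test is biased or has inflated type I error. Randomisation protects it; chance imbalance costs precision.

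**What to change.** In 11.1, replace the fallback t-test with a linear model fitted within each period: log seizure rate on treatment, with log pre-randomisation baseline seizure rate as covariate. Define the rate so that zero counts are covered, for example log((count + 0.5)/days), using the days actually observed because both the baseline and the treatment periods vary in length. Report the active/placebo rate ratio with its 95% CI.

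In 11.41, restate the effect, SD and power on that scale. If the present assumptions are read as rates of 0.55 and 0.85 of baseline, the effect is a ratio of 0.55/0.85 = 0.647, or −0.435 in natural logs. The residual SD after adjustment needs its own justification; the 25% does not carry over.

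The cost is one degree of freedom and a sentence in each section. No new data, visits or procedures are needed. The restated power may come out below 80% at 24 completers.
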